### **5.3 Rationale for Design of Trial**

The proposed pilot study will provide safety and efficacy preliminary data regarding singular and combined effects of two therapeutic approaches, intranasal insulin and treatment with the SGLT2i empagliflozin, to correct bioenergetic and vascular dysfunction in adults with preclinical AD and amnestic mild cognitive impairment (aMCI) or early AD.

### **5.4 Rationale for Biofluids**

The CSF biomarkers insulin, A $\beta$ 42, A $\beta$ 40, total tau and phospho-tau will be measured, as well as CSF markers of vascular function. Plasma levels of insulin and glucose will be also assessed. Plasma and CSF samples obtained in this study will be banked so that other putative biomarkers may be measured by qualified investigators in the future given adequate rationale and feasibility.

## **6.0 STUDY OVERVIEW**

The study will consist of a single site, randomized, double-blind trial comparing the effects of 4 weeks of INI (40 International Units q.i.d.), empa (10 mg q.d.) and combined INI and empa compared with placebo on CSF biomarkers and cognition. At study entry, participants will be randomized to one of 4 conditions: INI, empa, INI+empa, placebo. Participants who are cognitively normal but have abnormal elevations of brain amyloid (n=20) or who have MCI or early AD (n=40) will be enrolled. The primary outcome measure will consist of safety (treatment-related serious adverse events). Secondary measures will consist of CSF biomarkers, cognition, and cerebral blood flow. Exploratory measures will include continuous glucose levels and sleep quality as assessed with actigraphy.

### **6.1 Study Population**

A total of 60 adults who are 1) cognitively normal/amyloid positive (n=20) or 2) diagnosed with aMCI or early AD (n=40) will be enrolled in this trial. To determine eligibility, all participants will undergo cognitive assessment, physical and neurological examination, ECG, clinical/safety laboratory assessment, and interviews of the participant and study partner conducted by the investigators and staff of the Clinical Core of the Wake Forest Alzheimer's Disease Research Center (ADRC).

### **6.2 Diagnosis Criteria**

Diagnoses will be assigned by consensus of investigators from the Clinical Core of the Wake Forest ADRC using criteria specified by the NIA and Alzheimer's Association workgroups (Petersen, Doody et al. 2001, Albert, Dekosky et al. 2011).

Criteria for cognitively normal/amyloid positive adults:

- a) No evidence of significant cognitive impairment on objective testing
- b) Amyloid positivity as determined by amyloid PET (amyloid SUVR>1.21 or CSF A $\beta$ 42<600 pg/ml)

Diagnosis of aMCI or AD dementia requires:

- a) Diagnosis of amnestic mild cognitive impairment (MCI) or early AD according to NIA-Alzheimer's Association Criteria (CDR 0.5 or 1, MMSE>21)
- b) Amyloid positivity as determined by amyloid PET (amyloid SUVR>1.21 or CSF A $\beta$ 42<600 pg/ml)

### **6.3 Inclusion Criteria**

The following inclusion criteria will be used:

1. Age 55 to 85 (inclusive)
2. Fluent in English
3. Cognitively normal or diagnosis of aMCI or mild AD
4. Amyloid positive by PET or CSF criteria
5. Stable medical condition for 3 months prior to screening visit
6. Stable medications for 4 weeks prior to the screening and study visits (exceptions may be made on a case by case basis by study physician)
7. Clinical laboratory values must be within normal limits or, if abnormal, must be judged to be clinically insignificant by the study physician

### **6.4 Exclusion Criteria**

The following exclusion criteria will be used:

1. A diagnosis of dementia other than AD
2. History of a clinically significant stroke
3. Current evidence or history in past two years of epilepsy, head injury with loss of consciousness, any major psychiatric disorder including psychosis, major depression, bipolar disorder
4. Diabetes (type I or type II) insulin dependent and non-insulin dependent diabetes mellitus
5. Current or past regular use of insulin or any other anti-diabetic medication within 2 months of screening visit
6. History of seizure within past five years
7. Pregnancy or possible pregnancy
8. Use of anticoagulants, unless documentation received from prescribing clinician that anticoagulant medication can be held before LP, and approved by study clinician
9. Residence in a skilled nursing facility at screening
10. Use of an investigational agent within two months of screening visit

11. Regular use of alcohol, narcotics, anticonvulsants, anti-parkinsonian medications, or any other exclusionary medications (exceptions may be made on a case by case basis by study physician)

## **6.5 Recruitment and Retention Strategies**

Recruitment will occur primarily from the Clinical Core of the Wake Forest ADRC. Some participants may also be identified from community recruitment efforts or from recently completed studies.

## **7.0 STUDY TIMELINE**

The approximate timeline for this 18-month study is projected as follows: 1) approximately two months for study startup activities; 2) study visits will occur over a ten-month period; 3) CSF and blood analyses, data analyses and study dissemination will occur over the final 6 months.

## **8.0 DESCRIPTION OF STUDY VISITS**

The "Schedule of Study Procedures and Assessments" in Table 4 (located in section 23.0) provides an overview of study visit activities. Genotyping will occur at Screening for participants who have not previously received APOE genotypes through the ADRC.

### **8.1 Screening (Visit 1)**

The purpose of this visit is to determine study eligibility. Potential participants must sign an informed consent form and HIPAA Authorization prior to administration of any study-related procedures. After consent is obtained, participants will be given the MMSE, the CDR and Story Recall to determine study eligibility. Screening may be waived for participants who have received evaluations from the ADRC within the past 12 months. In addition, all cognitively normal participants must have amyloid PET or CSF Aβ42 results available from the ADRC or affiliated studies prior to screening.

Information regarding demographics, concurrent medications, medical history and adverse events will be gathered from the participant. Vital signs, height and weight will be measured. A brief physical and neurological examination (which include a nasal examination) and a resting ECG will be performed. The ECG report will be reviewed, signed, and dated by the investigator or a medically qualified staff member as delegated by the Principal Investigator. Those with clinically significant ECG findings will be referred for follow-up as deemed appropriate by the investigator. These procedures may be waived for participants who have received evaluations from the ADRC within the past 12-months.

Fasting blood will be drawn for routine clinical laboratory evaluations. If values are outside of the laboratory's normal range and determined clinically significant by the medically qualified study investigators, lab tests may need to be repeated and may be considered exclusionary for participation in the study. Blood samples will also be collected for ApoE genotyping and DNA storage.

### **8.2 Baseline Visit 1 (Visit 2)**

Results from all screening procedures must be reviewed and all inclusion/exclusion criteria must be met prior to proceeding to baseline. For participants whose screening visit was waived because they had received ADRC evaluations within the past 12-months will sign an informed consent form and HIPAA Authorization prior to administration of any study-related procedures.

According to the randomization schedule, the participant will be assigned to the insulin, empa, insulin+empa or placebo arm. On their first baseline visit they will receive the following:

- 1) Cognitive assessment
- 2) MRI (ADRC MRI may be used if done within 6 months of enrollment)
- 3) Insertion of the Libre Freestyle Pro continuous glucose monitor

- 4) Training on use of the Libre Freestyle Pro continuous glucose monitor
- 5) Training on how to use the intranasal delivery device and provision of saline to use with the device for the 1 week practice period (if applicable)
- 6) Training on how to record compliance
- 7) Training on use of the Empatica E4 actigraph for sleep assessment
- 8) PROMIS Sleep Disturbance and Sleep-Related Impairment Questionnaires
- 9) Patient Health Questionnaire-9 (PHQ-9)
- 10) General Anxiety Disorder Scale (GAD-7)
- 11) Nasal examination
- 12) Vital signs and weight
- 13) Collection of AEs and Con Meds

### **8.3 Baseline Visit 2 (Visit 3; one week after Baseline Visit 1)**

For the 2nd baseline visit which occurs one week after Baseline Visit 1, the following procedures will be administered:

- 1) Lumbar puncture will be performed in the morning after a minimum 8-hour overnight fast. After insertion of the spinal catheter, CSF will be collected immediately. Insulin (40 IU) will then be administered, additional CSF will be collected following administration, and then the spinal catheter will be withdrawn. Blood will be drawn immediately before and following the LP under fasting conditions. Participants will then receive a snack and instructions about post-lumbar puncture care. Site staff will call the participant within 24 hours from the lumbar puncture procedure to inquire about the participant's well-being and possible adverse events.
- 2) The ADCS-ADL-MCI and qDRS will be administered
- 3) The Libre Freestyle Pro continuous glucose monitor will be removed
- 4) The Empatica E4 actigraph and PROMIS sleep questionnaires will be collected
- 5) Device use and feasibility issues during the run-in period will be reviewed
- 6) Distribution of study drug and placebos (if applicable)
- 7) Nasal examination
- 8) Vital signs and weight
- 9) Collection of AEs and Con Meds

### **8.4 Re-supply Visit and Safety/Compliance Assessment 1 (Visit 4; one week after Baseline Visit 2)**

For the re-supply visit, the following procedures will be administered:

- 1) Device use and instructions will be reviewed
- 2) Collection of nasal drug vial and pill count
- 3) Distribution of study drug and placebos (if applicable)
- 4) Vital signs and weight
- 5) Collection of AEs and Con Meds

### **8.5 Phone Safety/Compliance Assessment 2**

Participants will receive a call from study staff 2 weeks after initiating treatment to monitor for adverse events and compliance.

### **8.6 Post-treatment Visit 1 (Visit 5)**

On their first post-treatment visit they will receive the following:

- 1) Cognitive assessment
- 2) MRI
- 3) Insertion of the Libre Freestyle Pro continuous glucose monitor
- 4) Provision of the Empatica E4 actigraph for sleep assessment

- 5) PROMIS Sleep Disturbance Questionnaires
- 6) Patient Health Questionnaire-9 (PHQ-9)
- 7) General Anxiety Disorder Scale (GAD-7)
- 8) Nasal examination
- 9) Vital signs and weight
- 10) Collection of AEs and Con Meds

## **8.7 Post-treatment Visit 2 (Visit 6; one week after Post-treatment Visit 1)**

On their second post-treatment visit which occurs 1 week after Post-treatment Visit 1 they will receive the following:

- 1) Lumbar puncture will be performed in the morning after a minimum 8-hour overnight fast. After insertion of the spinal catheter, CSF will be collected immediately. Insulin (40 IU) will then be administered, additional CSF will be collected following administration, and then the spinal catheter will be withdrawn. Blood will be drawn immediately before and following the LP under fasting conditions, including routine clinical laboratory evaluations. Participants will then receive a snack and instructions about post-lumbar puncture care. Site staff will call the participant within 24 hours from the lumbar puncture procedure to inquire about the participant's well-being and possible adverse events.
- 2) The ADCS-ADL-MCI and qDRS will be administered
- 3) The Libre Freestyle Pro continuous glucose monitor will be removed
- 4) The Empatica E4 actigraph and sleep questionnaire will be collected
- 5) Nasal examination
- 6) Vital signs and weight
- 7) Collection of AEs and Con Meds
- 8) Collection of nasal drug vials and pill count

Order of administration of procedures may occasionally vary due to scheduling constraints, as approved by the study clinicians.

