## **10.0 STUDY METHODS**

### **10.1 Safety Assessments**

At each study visit, all participants will undergo a nasal examination and any occurrence of adverse events will be reviewed and documented; concomitant medications will be recorded as well. In addition, 24 hours after the Lumbar Puncture, each study participant, or a person designated to speak for them will be contacted by phone to confirm the participant's well-being and queried about any new adverse events. All adverse events will be reported to the study MD for review.

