### **13.5 Lumbar Puncture**

Lumbar puncture may be associated with pain during the performance of the procedure. This is usually temporary and confined to the lower back. Headache may occur in about 5% of elderly people who undergo lumbar puncture. Less commonly, in about 1-4% of participants, a persistent low-pressure headache may develop, probably due to leakage of CSF. Lower rates of post-LP headache have been noted in elderly patients, and when atraumatic (Sprotte) needles are used. If a post-LP headache persists it may need additional treatment, e.g. with fluids and analgesics. Uncommonly a blood patch (injection of some of the participant's blood to patch the CSF leak) may be needed. Potential but rare risks of lumbar puncture include infection, damage to nerves in the back, and bleeding into the CSF space. The risk of these is much less than 1%.

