### **20.4 Data and Safety Monitoring Plan**

The principal investigator and study clinician(s) will be responsible for the overall monitoring of the data and safety of study participants, with assistance by members of the study staff. Participants will be screened at the beginning of the study and will be monitored carefully at each study visit. Participants will be queried for serious adverse events (SAEs) and selected AEs (those temporally related to study procedures) at each study visit. All SAEs and selected AEs will be recorded on an AE case report form. Based on the nature of the AE, study clinicians will determine the severity of the event and association with the study. All serious adverse events will be reported. Serious adverse events are defined as events that are (1) life-threatening or fatal, (2) result in severe or permanent disability, or (3) require hospitalization. SAEs will be reported to the IRB within 7 days of investigator

knowledge of the event if they are related and unanticipated (i.e. if they qualify as an unanticipated problem). All serious adverse events will be followed until resolution, or 90 days after study participation has been terminated.

"Severity" of events will be graded according to the following guidelines:

1. Mild: The participant is aware of, but can easily tolerate, the event
2. Moderate: The discomfort of the event is severe enough to interfere with some usual activities
3. Severe: The participant is incapacitated, and unable to perform most or all usual activities

The "study-relatedness" will be assigned according to the following guidelines:

1. Definitely Related: The reaction follows a reasonable temporal sequence and is known to be an effect of participation or a procedure
2. Possibly Related: The reaction follows a reasonable temporal sequence, and current medical knowledge does not preclude a relationship between participation or procedure and the event.
3. Unlikely: Little evidence to suggest a causal relationship (e.g. the event did not occur within a reasonable time after administration of the trial medication) or another reasonable explanation for the event (e.g. another clinical condition or other concomitant treatment).
4. Definitely Unrelated: Current medical knowledge precludes a causal relationship between participation or procedure and the event or the cause of the reaction is known to be other than participation or procedure.

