23.0 TABLE 4: SCHEDULE OF PROCEDURES AND ASSESSMENTS

Visit #	1	2	3	4		5	6
Visit Name	Screen 	Baseline V1	Baseline V2	Re-supply	Phone	Post-Treatment V1	Post-Treatment V2
Informed Consent	X	X 					
Demographics	X	X 					
Medical History	X	X 					
Concomitant Meds	X	X	X	X	X	X	X
Adverse Events	X	X	X	X	X	X	X
Nasal Exam	X	X	X			X	X
Physical and Neurological Exam		X					
Vital Signs	X	X	X	X		X	X
Height	X						
Weight	X	X	X	X		X	X
ECG	X						
Cognitive Assessment	X	X	X			X	X
Questionnaires	X	X	X			X	X
Aptar CPS Device & Compliance Training		X					
Compliance Assessment			X	X	X	X	X
Study Drug Dispensed			X 	X			
Actigraphy		X				X	
Continuous Glucose Monitor (CGM) Placement		X				X	
Blood Draw	X		X				X
- Clinical Labs	X		X				X
- ApoE Genotyping   DNA Banking	X						
- Biomarkers   Plasma   Serum   Sample Banking			X				X
LP			X				X

- CSF Biomarkers   Banking			X				X
- Post- Procedure Safety Telephone Check			X				X
MRI		X 				X	

MRI can be excluded if done within 6 months of enrollment

Screening may be waived if evaluations have been performed within the last 12 months

Will be performed if participant was eligible to skip Screening

Study drug may be re-dispensed as needed (if applicable)

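### The last scheduled safety contact is one call about 24 hours after the Visit 6 lumbar puncture, so events that begin later are found only if volunteered

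*Combined protocol and SAP*

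**What the plan says.** Section 8.7 makes Visit 6 the final visit. It contains the second LP with 40 IU of insulin given during it, collection of adverse events, return of nasal vials and the pill count. It also contains the last safety laboratory draw: "Blood will be drawn immediately before and following the LP under fasting conditions, including routine clinical laboratory evaluations". The only later contact is a telephone call: "Site staff will call the participant within 24 hours from the lumbar puncture procedure". Section 10.1 describes the same call: "24 hours after the Lumbar Puncture, each study participant, or a person designated to speak for them will be contacted by phone". Table 4 shows it as "Post- Procedure Safety Telephone Check" under Post-Treatment V2, which is the last column.

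After the first LP the schedule continues. Section 8.4 places the re-supply visit ("Visit 4; one week after Baseline Visit 2") and collects adverse events there. A phone assessment, Visit 5 and Visit 6 follow.

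On follow-up, section 16.2 requires known adverse events to be followed until they subside or stabilise, or the participant can no longer be reached. Section 20.4 adds: "All serious adverse events will be followed until resolution, or 90 days after study participation has been terminated". Section 17.2 opens reporting of serious events at consent and gives no closing date. Section 13.5 puts persistent low-pressure headache at about 1-4% of participants and headache of any kind at about 5%. It notes "If a post-LP headache persists it may need additional treatment" and lists infection, nerve damage and bleeding as rare. The synopsis defines the primary outcome as the number of treatment-related serious adverse events.

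**The concern.** A safety endpoint depends on how long and how actively events are sought. Here active questioning stops about a day after a second invasive procedure and, it appears, about a day after the last dose. An event that begins after the call enters the record only if someone volunteers it. That is a weak route in this population: 40 of the 60 participants are to have aMCI or early AD, and section 10.1 itself allows another person to answer the safety call for them.

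At stake is the completeness of the safety record, including the primary outcome, for the end of treatment and for half of the planned LPs. A report of few or no late events would partly reflect that nobody asked.

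**Working it through.** The plan gives no figure for this point, and section 12.1 says that no power calculation was done, so there is nothing to reproduce. The check traces the contacts and then puts a scale on the events that could fall in the gap.

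**1. Contacts after each LP**

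| | First LP (Visit 3) | Second LP (Visit 6) |
|---|---|---|
| Call at about 24 hours | yes | yes |
| Adverse events collected about one week later | yes (Visit 4) | no |
| Later scheduled contacts | phone assessment, Visits 5 and 6 | none |

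The empagliflozin safety section (13.1) mentions two phone safety/compliance calls. Sections 8.4 and 8.5 number the two safety/compliance assessments and place them one and two weeks into treatment. Nothing puts either one after Visit 6.

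**2. Does dosing run to Visit 6?** Drug containers are collected and pills counted at Visit 6 (8.7). The glucose monitor is fitted at Visit 5 and removed at Visit 6, and the section on combined safety (13.2) says that monitoring covers the last week of treatment. Together these put the end of home dosing at about Visit 6. This is an inference, because Visits 5 and 6 are both titled post-treatment. If home dosing stopped at Visit 5, about a week of observation would follow it. The 40 IU given during the Visit 6 LP would still have only the one call after it.

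**3. Does the stated participation time fill the gap?** Counting from Baseline Visit 1, Baseline Visit 2 is at week 1.

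- If Visit 6 ends the four treatment weeks: 1 + 4 = week 5.
- If Visit 5 ends them: 1 + 4 + 1 = week 6.
- The synopsis gives 8 weeks of participation, which leaves 8 − 5 = 3 or 8 − 6 = 2 weeks. Screening may use some of this, but no contact is scheduled in what remains.

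**4. Do the follow-up clauses detect new events?** Sections 16.2 and 20.4 both start from an event already identified. Section 17.2 requires prompt reporting once an event is learned of. None of the three schedules a contact at which a new event would be learned of.

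**5. Scale of LP events that could occur** (n = 60, rates from section 13.5). Expected number = n × p; chance of at least one = 1 − (1 − p)^n.

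- Persistent headache, rate applied to the final LP: 60 × 0.01 = 0.6 and 60 × 0.04 = 2.4. Chance of at least one: 1 − 0.99^60 = 45% and 1 − 0.96^60 = 91%.
- Same rate read as covering both LPs, with half falling after the second: 60 × 0.005 = 0.3 and 60 × 0.02 = 1.2. Chance of at least one: 1 − 0.995^60 = 26% and 1 − 0.98^60 = 70%.
- Any headache at 5%, applied to the final LP: 60 × 0.05 = 3.0. Chance of at least one: 1 − 0.95^60 = 95%.

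Section 13.5 words the persistent-headache rate per participant and does not say how many LPs it covers, so both readings are shown. These are occurrences. The number that would begin after the call and go unreported needs onset times, which the documents do not give.

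**The case against.** **LP harms are not the primary outcome.** The primary outcome is treatment-related serious events, whereas section 13.5 lists headache, infection and nerve damage as risks of the procedure. Every arm has the same LP and the same call. A reader might infer that the short window biases the comparison between arms. The documents do not support that: what is shown is incomplete ascertainment common to all arms.

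**The headache figures do not count missed events.** A headache reported at the call must be followed under section 16.2, so its persistence would be recorded. Only onset after the call is exposed. By the definition of a serious event in section 20.4 (life-threatening or fatal, severe or permanent disability, or hospitalisation), most such headaches would not qualify. This stands, so the figures are used for scale only.

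**Delayed harms.** A reader might infer that the protocol names harms of delayed onset, or that the plan systematically leaves out late events. It does neither. Section 13.5 says that a headache may persist and gives no onset times. Ketoacidosis is tied to a subset of patients with Type 2 diabetes, and diabetes is excluded.

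**Final laboratory values.** A reader might infer that an abnormal Visit 6 result cannot become an adverse event. It can: sections 10.4, 16.1 and 16.2 provide for clinical review, possible repeat testing, recording as an event and follow-up. Only a scheduled contact at which the outcome is noted is lacking.

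**Collection has no stated end.** Section 17.2 sets no closing date, so a later serious event that comes to light can still be reported. That is right, and a careless fix could narrow it. Every final procedure also lacks a next visit, and Visit 4 is a re-supply visit that was not designed as LP follow-up, so the one-week interval is a convenient model and not a rule. None of this supplies a contact that asks about new events.

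**Conclusion.** The point holds as a gap in solicited safety ascertainment. The last scheduled contact is one call about 24 hours after the Visit 6 LP, and events beginning after it, including treatment-related serious events, are liable to be missed unless volunteered. All 60 planned second LPs are affected, against a further solicitation at about one week for the first LPs.

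The number of events lost cannot be derived from the documents. The 0.6 to 2.4 persistent headaches (0.3 to 1.2 if the rate covers both LPs) show only that such events are plausible in a trial of this size. The conclusion assumes that all 60 participants have the second LP and that home dosing continues to about Visit 6. The LP part of the point does not depend on the dosing assumption. This is an inexpensive improvement to a pilot whose primary outcome is safety, and it does not invalidate the trial.

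**What to change.** - Add one adverse-event call after Visit 6 to section 8.7 and as a column in Table 4. About one week would mirror the interval after the first LP; the length is for the sponsor to set.
- At that call, ask the participant or the designated person about new adverse events and serious adverse events, including LP symptoms, and note the outcome of any clinically significant Visit 6 laboratory value.
- State in section 17.2 when solicited collection ends. Say in the same place that serious events that become known later are still reported, and that the follow-up in section 20.4 is unchanged.

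The cost is about 60 short calls by existing staff, one schedule column, and slightly longer contact with participants. Dosing, eligibility and treatment are untouched.
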